6.2.5.2 Follow-up for Overall Survival

Sponsor has decided that as of this protocol amendment acknowledgement no further survival status follow-up will be collected.

6.2.5.3 Trial completion for an individual patient

A patient is considered to have completed the trial in case any of the following applies:

- Completion of planned follow-up period
- Lost to follow-up
- Withdrawal to be followed-up
- Death

At the earliest of the above criteria, the Patient Completion (PC) information should be entered in the CRF.

7. STATISTICAL METHODS AND DETERMINATION OF SAMPLE SIZE

7.1 STATISTICAL DESIGN - MODEL

This is a Phase I, open-label, dose-escalating trial to determine the Recommended Phase 2 Dose (RP2D) of BI 836880 in combination with ezabenlimab in patients with locally advanced or metastatic non-squamous NSCLC during or after first line platinum-based chemotherapy or CPI monotherapy treatment or the combination of CPI and chemotherapy. In addition, the safety and efficacy of BI 836880 in combination with ezabenlimab will be assessed.

7.1.1 Statistical design - Part 1 (dose escalation)

7.1.1.1 Combination BLRM

The objective of Part 1 of the trial is to determine RP2D of BI 836880 in combination with ezabenlimab based on MTD, patients are entered sequentially into escalating dose cohorts. The Part 1 dose finding will be guided by a Bayesian 5-parameter logistic regression model with overdose control ([R13-4803](#), [R15-4233](#)).

The logistic regression model is defined as follows. Let $\pi_{1,d1}$ be the probability of having a DLT when giving dose d_1 of BI 836880 as monotherapy, and $\pi_{2,d2}$ be the probability of having a DLT when giving dose d_2 of the combination partner ezabenlimab as monotherapy, respectively.

A logistic regression model is used to model the dose-toxicity relationship for each component individually:

BI 836880 part:

$$\text{logit}(\pi_{1,d1}) = \log(\alpha_1) + \beta_1 \log(d_1/d_1^*)$$

Ezabenlimab part:

$$\text{logit}(\pi_{2,d2}) = \log(\alpha_2) + \beta_2 \log(d_2/d_2^*)$$

where $\text{logit}(\pi) = \log(\pi / (1 - \pi))$, the reference doses $d_1^* = 720$ mg and $d_2^* = 240$ mg are set for BI 836880 and ezabenlimab, respectively.

Assuming no toxicity interaction between the two compounds, the probability of a DLT when giving the combination of dose d_1, d_2 is obtained as

$$\pi_{12,d1,d2}^0 = \pi_{1,d1} + \pi_{2,d2} - \pi_{1,d1}\pi_{2,d2}$$

with corresponding odds

$$\text{odds}(\pi_{12,d1,d2}^0) = \pi_{12,d1,d2}^0 / (1 - \pi_{12,d1,d2}^0)$$

In order to account for a potential positive (higher toxicity than expected under independence) or negative (lower toxicity than expected under independence) interaction

between BI 836880 and ezabenlimab, a dose-dependent interaction term $-\infty < \eta < \infty$ is introduced to the model by the following definition:

odds($\pi_{12,d1,d2}$) = odds($\pi_{12,d1,d2}^0$) $\exp(\eta \cdot d_1/d_1^* \cdot d_2/d_2^*)$
and $\pi_{12,d1,d2}$ is used in the likelihood

$$r_{d1,d2} \sim \text{Binomial}(n_{d1,d2}, \pi_{12,d1,d2})$$

where $r_{d1,d2}$ denotes the a variable describing the observed number of DLTs from $n_{d1,d2}$ patients at the dose combination d_1, d_2 .

Since a Bayesian approach is applied, prior distributions f for each of the parameter vectors $\theta_1 = (\log(\alpha_1), \log(\beta_1))$, $\theta_2 = (\log(\alpha_2), \log(\beta_2))$ and for the interaction term η need to be specified. The prior distributions for θ_1 and θ_2 will be specified as mixtures of two multivariate normal distributions, i.e.

$$a(\theta_k) = a_{1,k} f_1(\theta_k) + a_{2,k} f_2(\theta_k)$$

with

$a_{1,k}, a_{2,k}$ the prior mixture weights, $k=1,2$ and

$$f_i(\theta_k) = \text{MVN}(\mu_{ik}, \Sigma_{ik}) \quad (k=1,2),$$

the multivariate normal distribution of the i -th component with mean vector μ_{ik} and covariance matrix Σ_{ik} , where

$$\Sigma_{ik} = \begin{pmatrix} \sigma_{ik,11}^2 & \sigma_{ik,11}\sigma_{ik,22}\rho_{ik} \\ \sigma_{ik,11}\sigma_{ik,22}\rho_{ik} & \sigma_{ik,22}^2 \end{pmatrix}$$

Mixture prior distributions have the advantage that they allow for specification of different logistic dose-toxicity curves, therefore making the prior more robust.

A weakly informative normal prior distribution will be used for η .

The estimated probability $\pi_{12,d1,d2}$ of a DLT at each dose combination d_1, d_2 from the model will be summarized using the following intervals:

Under dosing: [0.00, 0.16)

Targeted toxicity: [0.16, 0.33)

Over dosing: [0.33, 1.00]

The BLRM-recommended dose combination for the next cohort is the level with the highest posterior probability of the DLT rate falling in the target interval [0.16, 0.33) among the dose combinations fulfilling the EWOC principle. Per EWOC it should be unlikely (i.e., <25% posterior probability) that the DLT rate at the dose combination will exceed 0.33. However, the maximum allowable dose increment for the subsequent cohort will be no more than 100% for each compound.

The MTD may be considered reached if one of the following criteria is fulfilled:

1. The posterior probability of the true DLT rate in the target interval [0.16, 0.33) of the MTD is above 50%, OR
2. At least 8 patients have been treated in the study, of which at least 6 at the MTD.

Prior derivation:

By the time BLRM is analyzed, safety data for ezabenlimab are expected to be available from BI Study 1381.1 and preliminary safety data for BI 836880 will be available from the study 1336.1. The information can be incorporated into the prior derivation meta-analytic predictive (MAP) approach. Exact details on the evaluations of the model using hypothetical data scenarios and operating characteristics are provided in the statistical appendix.

For illustrative purposes only, we assume the following hypothetical data on BI 836880 (Table 7.1.1.1: 1) and ezabenlimab (Table 7.1.1.1: 2) are available and describe how prior distribution is derived using the MAP approach. However, at the time when BLRM is performed for 1336.11, actual data available will be used instead.

Table 7.1.1.1: 1 Hypothetical data for BI 836880

Dose BI 836880 (mg)	N of patients treated	N of patients with DLTs during MTD evaluation period	N of patients with CTCAE Grade ≥ 3 hypertension and require medical intervention within all cycles or DLTs during MTD evaluation period
40	2	0	0
120	2	0	1
360	2	0	1
720	7	0	2
1000	5	1	3

Table 7.1.1.1: 2 Hypothetical data for ezabenlimab

Dose ezabenlimab (mg)	N of patients treated	N of patients with DLTs during MTD evaluation period
80	3	0
240	6	0
400	3	0

The following steps were used to derive the prior distributions for all parameters:

For θ_1 :

1. The meta-analytic-predictive prior was derived using the DLTs information of BI 836880 from BI Study 1336.1. Small between study heterogeneity is assumed. This mixture component was assigned 80% weight.
2. A second meta-analytic-predictive prior was derived using the number of patients with CTCAE Grade ≥ 3 hypertension and require medical intervention within all cycles or DLTs during MTD evaluation period from Study 1336.1. Small between study heterogeneity is assumed. This component was added with 20% weight.

For θ_2 :

1. The meta-analytic-predictive prior was derived using the DLTs information of ezabenlimab from BI study 1381.1. Small between study heterogeneity is assumed. This mixture component was assigned 90% weight.
2. A high-toxicity weakly-informative component was added with 10% weight based on the a priori assumption that the median DLT rate at the starting dose of 80 mg would equal 3% and the median DLT rate at 240 mg would equal 50%. This yields $\mu_{22} = 0$, 1.151). The standard deviations were set such that large uncertainty about the parameter means is reflected, and the correlation was set to 0, thus yielding $\sigma_{22,11} = 2$, $\sigma_{22,22} = 1$ and $\rho_{22} = 0$, respectively.

The prior distribution for η will be based on the a priori assumption of positive interaction between the two compounds, a normal distribution with mean 0 and standard deviation 0.707 was chosen. At the starting dose combination, the corresponding 95% prior interval covers an approximately 4-fold increase (or decrease) in the odds of a DLT over no interaction.

A summary of the prior distribution is provided in Table 7.1.1.1: 3. Additionally, the prior probabilities of DLT at different doses, as well as the corresponding probability of under-, targeted and overdosing, are shown in [Table 7.1.1.1: 4](#).

Table 7.1.1.1: 3 Parameters for prior distributions

Parameter	Means, standard deviations, correlation	Mixture weight
log(α_1), log(β_1): component 1	-1.936, 0.078, 0.644, 0.863, -0.072	0.80
log(α_1), log(β_1): component 2	-0.338, -0.592, 0.496, 0.680, 0.135	0.20
log(α_2), log(β_2): component 1	-3.007, -2.291, 0.802, 1.002, 0.003	0.90
log(α_2), log(β_2): component 2	-0, 1.15, 2, 1, 0	0.10
H	0, 0.707, n/a	n/a

Table 7.1.1.1: 4 Prior probabilities of DLTs

Dose (mg)	Dose (mg)	Probability of true DLT rate in			Descriptive Statistics		Quantiles		
BI 836880	Ezabenlimab	[0,0.16)	[0.16,0.33)	[0.33,1]	Mean	StD	2.5%	50%	97.5%
360	80	0.612	0.250	0.138	0.174	0.141	0.024	0.128	0.533
360	240	0.535	0.272	0.193	0.214	0.192	0.028	0.149	0.813
500	80	0.527	0.299	0.174	0.200	0.147	0.037	0.153	0.573
500	240	0.452	0.308	0.239	0.242	0.199	0.035	0.177	0.829
720	80	0.354	0.409	0.237	0.247	0.154	0.063	0.201	0.634
720	240	0.338	0.328	0.334	0.292	0.214	0.041	0.231	0.857
1000	80	0.204	0.408	0.388	0.316	0.180	0.078	0.274	0.741
1000	240	0.261	0.269	0.470	0.363	0.249	0.038	0.309	0.917

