3. DESCRIPTION OF DESIGN AND TRIAL POPULATION

3.1 OVERALL TRIAL DESIGN AND PLAN

This is a Phase I, non-randomized, uncontrolled, open-label, dose escalating study of BI 836880 administered in combination with ezabenlimab intravenously every 3 weeks. The eligible patient population will be CPI naïve and experienced patients with locally advanced or metastatic non - squamous NSCLC who progressed during or after first line platinum-based chemotherapy or CPI monotherapy treatment or the combination of CPI and chemotherapy in Part 1. Part 2 will have additional expansion cohorts.

Part 1:

Dose escalation of BI 836880 in combination with ezabenlimab in patients with locally advanced or metastatic non-squamous NSCLC who progressed during or after first line (in case of checkpoint inhibitor naïve patients) platinum-based therapy or relapsed after completion of at least 2 cycles (in case of checkpoint inhibitor relapsing patients) of platinum-based chemotherapy and a checkpoint inhibitor treatment (monotherapy or in combination with chemotherapy).

Dose escalation will start at combination of BI 836880 360mg and ezabenlimab 240mg and will be guided by Bayesian Logistic Regression Model (BLRM) [Section 7](#).

At the first dose level, the first patient will be treated and observed for at least 15 days before allowing the second patient to receive BI 836880 and ezabenlimab infusions.

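### The interaction prior N(0, 0.707) gives a 2-fold, not 4-fold, 95% odds range at the starting dose combination and does not assume positive interaction

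*Protocol*

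**What the plan says.** Section 7.1.1.1 builds the DLT probability of the combination from the two single-agent curves under independence. It then multiplies the odds by exp(η × d1/720 × d2/240), where 720 mg and 240 mg are the reference doses of BI 836880 and ezabenlimab. The term η is introduced to cover "potential positive (higher toxicity than expected under independence) or negative (lower toxicity than expected under independence) interaction".

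Further on in the same section, the prior for η is said to be "based on the a priori assumption of positive interaction between the two compounds", and "a normal distribution with mean 0 and standard deviation 0.707 was chosen". The last row of Table 7.1.1.1: 3 repeats 0 and 0.707. The text then describes what this prior implies: "At the starting dose combination, the corresponding 95% prior interval covers an approximately 4-fold increase (or decrease) in the odds of a DLT".

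Section 3.1 fixes the start: "Dose escalation will start at combination of BI 836880 360mg and ezabenlimab 240mg".

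Escalation is limited to combinations with less than 25% posterior probability that the DLT rate exceeds 0.33. Section 7.3.1.1 provides for the model to be rerun to re-evaluate the MTD and RP2D.

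**The concern.** The section makes two statements about the interaction prior, and neither follows from the prior that it then specifies.

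- **Width.** The 4-fold range is placed at the starting combination. The interaction term is dose-dependent, and the starting BI 836880 dose is half the reference dose, so the range there must be narrower than at the reference combination.
- **Direction.** A prior resting on positive interaction would put more weight on the combination being more toxic than independence predicts. A normal centred on 0 does not.

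The interaction prior feeds the overdose check directly. A reader of this section would believe that the model entered the first dose level with wider allowance for combination toxicity than it had, and with a tilt towards excess toxicity. If the rerun or the trial report carries the description forward, that belief goes with it.

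**Working it through.** **Inputs**

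- Odds multiplier exp(η × d1/720 × d2/240), Section 7.1.1.1.
- η ~ N(0, SD 0.707), Section 7.1.1.1 and Table 7.1.1.1: 3.
- Starting combination 360/240 mg, Section 3.1.
- Remaining prior parameters and mixture weights, Table 7.1.1.1: 3.
- Stated overdose probabilities, Table 7.1.1.1: 4 (prior) and Table 10.6.1: 1 (data scenarios).

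**Step 1. The stated 4-fold figure.** The 95% odds factor is exp(1.96 × SD × d1/720 × d2/240).

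| Combination (mg) | d1/720 × d2/240 | 95% odds factor |
|---|---|---|
| 360/240 (start) | 0.500 | exp(1.96 × 0.707 × 0.500) = 2.00 |
| 500/240 | 0.694 | exp(1.96 × 0.707 × 0.694) = 2.62 |
| 720/240 (reference) | 1.000 | exp(1.96 × 0.707 × 1.000) = 4.00 |

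Other readings of 0.707 do not restore the figure at 360/240: as a variance it gives 2.28, and as a precision 3.21. Conversely, ln 4 / 1.96 = 0.707, which is exactly the SD that yields 4-fold at the reference combination.

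**Step 2. Direction.** For a normal with mean 0, P(η > 0) = 0.50. The prior is centred on no interaction.

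**Step 3. Which prior do the tables use?** The full prior of Table 7.1.1.1: 3 was simulated with 2 million or more draws. The scenario data were then applied by weighting each draw by its binomial likelihood.

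| Probability of overdose | Protocol | N(0, 0.707) |
|---|---|---|
| Prior, 360/240 | 0.193 | 0.199 |
| Prior, 500/240 | 0.239 | 0.246 |
| Prior, 720/240 | 0.334 | 0.342 |
| Scenario 1A, at 720/240 | 0.210 | 0.210 |
| Scenario 1B, at 360/240 | 0.226 | 0.224 |
| Scenario 1C, at 500/240 | 0.133 | 0.132 |
| Scenario 2D, at 500/240 | 0.188 | 0.184 |
| Scenario 3C, at 720/240 | 0.168 | 0.170 |
| Scenario 3D, at 720/240 | 0.222 | 0.221 |

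The tables were produced with N(0, 0.707), to within small differences.

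**Step 4. What the stated width would require.** A 4-fold range at 360/240 needs SD = ln 4 / (1.96 × 0.5) = 1.415. At 720/240 that SD gives a factor of exp(1.96 × 1.415) = 16.0. With mean 0 and this SD:

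| Probability of overdose | SD 0.707 | SD 1.415 |
|---|---|---|
| Prior, 360/240 | 0.199 | 0.228 |
| Scenario 1A, at 720/240 | 0.210 | 0.256 |
| Scenario 1B, at 360/240 | 0.224 | 0.257 |
| Scenario 3D, at 720/240 | 0.221 | 0.295 |

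The starting combination would still pass before any data. The three scenario results, all shown as allowed in Table 10.6.1: 1, would exceed 25%.

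The operating characteristics in Table 10.6.2: 2 were not re-simulated.

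**The case against.** The strongest reply is that these are two slips of wording with no effect on the model. The 4-fold figure is exact at the reference combination, so the likeliest cause is that starting was written where reference was meant, with one wrong adjective besides. The surrounding text limits the damage: the model section allows interaction in either direction, the prior is called weakly informative, and the disputed sentence itself mentions a decrease. Most of this stands, and it is why the numeric prior and the tables are not in question.

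A reader might go further and infer that overdose control in this trial is less cautious than the protocol reports. The documents do not support that. The prior table, the tabulated prior probabilities and the checked data scenarios all agree with N(0, 0.707), and the 25% rule is unaffected. The model is less cautious only than the sentence describing it. Nor can the size of a missing positive shift be worked out, because the protocol gives no positive mean; any value would be the reader's own.

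Two more points count against making much of this. Section 4.1.2.2 records that the Part 2 dose has been selected, with a role for all available data and not the model alone. Section 7.1.1.1 also says that the single-agent data behind the priors are hypothetical and will be replaced, so the scenario probabilities above are illustrative, and 0.256 and 0.257 lie only just over the limit. What the reply does not remove is that the model is still to be rerun, and the text does not say that the prior for η will change.

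**Conclusion.** The description of the interaction prior is wrong on both counts. The 95% odds factor at the starting combination is about 2.0, not about 4; it is 2.6 at 500/240 and 4.0 at 720/240. The prior assumes no interaction on average, with probability 0.50 on each side. These results need only the model formula, the reference doses, the starting dose and the stated SD, so they are firm.

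The fault is in a stated property of the safety model and not in its tabulated results. It is more than cosmetic because the two possible meanings lead to different decisions: with the SD that the sentence implies, scenarios 1A, 1B and 3D move from below 25% to 0.256, 0.257 and 0.295. Those three values assume the illustrative single-agent priors of Table 7.1.1.1: 3 and a mean of 0. No past escalation decision is called into question by this point. What remains open is the rerun under Section 7.3.1.1 and how the prior is reported.

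**What to change.** - In Section 7.1.1.1, describe the prior for η as symmetric and centred on no interaction, with 95% odds factors of about 2.0, 2.6 and 4.0 at 360, 500 and 720 mg BI 836880 with 240 mg ezabenlimab. Delete the word positive.
- In Section 7.3.1.1, state which prior for η the rerun uses, and report one further run with mean 0 and SD 1.415 beside it, giving the overdose probability under each.

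The cost is a correction to the prior description, a short addition on the rerun and one extra model run. The downside is that the overdose probability in the extra run may look less favourable.

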7.1.1.2 Statistical model assessment

The model was assessed using 2 different metrics:

1. Hypothetical data scenarios: for various potential data constellations as they could occur in the actual trial, the maximal doses allowed in the next cohort by the model are investigated. Data scenarios thus provide a way to assess the ‘on-study’ behavior of the model.
2. Simulated operating characteristics: these illustrate for different assumed true dose toxicity relationships, how often a correct dose would be declared as MTD by the model. They are a way to assess the ‘long-run’ behavior of the model.

In summary, the model showed very good behavior as assessed by these metrics. More details can be found in [Appendix 10.5](#). The simulations were conducted using R Version 3.3.2 in conjunction with WinBUGS Version 1.4.

7.1.2 Statistical design - Part 2 (dose expansion cohorts)

To effectively use the information from these patients’ cohorts in the assessment of the efficacy, a Bayesian hierarchical model (BHM) approach ([R13-4803](#)), which assumes full exchangeability of model parameters and allows borrowing information across patients’ cohorts, will be used to analyze the response rate endpoints.

The BHM has 2 main components: a data model and a parameter model, as well as priors for the parameter model. The data model is a binomial sampling model

$$r_j | n_j \sim \text{Binomial}(n_j, p_j), j = 1, 2, 3, \dots$$

where n_j and r_j are the number of patients and the corresponding number of patients with response in each patient cohort. The parameter model for the log-odds parameters, including an adjustment for the target rates

$$\theta_j = \log\left(\frac{p_j}{1-p_j}\right) - \log\left(\frac{\tilde{p}_j}{1-\tilde{p}_j}\right)$$

is specified as

$$\theta_j | \mu, \tau \sim N(\mu, \tau^2), j = 1, 2, 3, \dots$$

where \tilde{p}_j is the target response rate, μ denotes the “overall” mean of θ_j and τ determines the inter-cohort heterogeneity.

Prior distribution

A non-informative normal distribution with mean 0 and standard deviation of 2 is specified for the mean μ . For the inter-cohort heterogeneity parameter τ , a half normal distribution with parameter 1 is used which is a very conservative assumption regarding between-cohort variability and hence leads to only little borrowing of data across patient cohorts because there is little prior information on the strength of the correlation between the treatment effects across cohorts.

Additional analysis of cohort F

Patients in cohort F starting treatment after 15-Jul-2021 (in accordance with protocol version7) will be considered as stage II patients whereas patients with treatment start date before 15-Jul-2021 are considered as stage I patients.

For cohort F, the first 30 patients treated in stage I were included in the aforementioned BHM model and the decision was made to expand this cohort. Patients to be treated in stage II will not be included in the BHM analysis. A separate Bayesian model will be used to analyze the stage II patients' data, while incorporating the stage I patients' data in a robust meta-analytic predictive (MAP) prior as specified below.

The R package “RBesT” and functions `gMAP()`, `automixfit()` and `robustify()` are used to derive the robust MAP prior. At the first step, a MAP prior is derived with information from stage I (12/30 responders) together with a specification of weakly informative prior $N(0,2)$ for the intercept parameter and $HN(0.125)$ for variance for moderate heterogeneity between stage I and stage II. At the second step, a weakly-informative component of Beta (0.6, 1.4) is added with 10% weight to make the MAP prior more robust by implementing the two-component mixture structure (see Table 7.1.2: 1). The effective sample size of this robust MAP prior is estimated to be 14.

Table 7.1.2: 1 Robustified MAP prior

Parameter*	Beta parameters (a,b)	Mixture weight
Component 1	10.66, 15.82	0.90
Component 2	0.60, 1.40	0.10

After all of the approximately 30 patients are treated in stage II and sufficiently evaluable for efficacy, the posterior distribution will be derived including the stage I data in a beta-binomial conjugate model with the above robust MAP prior. The Bayesian decision criterion,

to analyze the objective response rate (ORR) of the 30 additional patients in stage II is specified as:

$$\text{posterior probability } (p_{\text{ORR}} > 0.25 | \text{Data from stage II}) > 0.85$$

The threshold of 0.25 for the objective response is selected based on the historical data of 18% and 32.2% response rates reported for pembrolizumab ([R21-2759](#)) and for combination treatment of nivolumab and ipilimumab ([R21-2758](#)) in sorafenib pre-treated patients.

A minimum observed response rate of 27% (naïve estimate) among 30 patients at stage I is required to pass this criterion. A further expansion of this cohort may be considered through a protocol amendment if this Bayesian decision criterion is passed.

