7.3.1 Primary endpoint analyses

7.3.1.1 Primary endpoint analyses for Part 1

In order to identify the MTD(s) and the recommended dose(s) for Part 2 of the trial, the number of patients with DLTs at each dose combination during the Part 1 MTD evaluation period (the first cycle of the BI 836880 plus ezabenlimab combination) must be presented by descriptive statistics. Patients who discontinue during the first treatment cycle for reasons other than a DLT will be excluded from the determination of the MTD. In addition, the number of patients with DLTs that occurred during the entire treatment period will be summarized at each dose level. The BLRM will be rerun to re-evaluate the MTD and RP2D together with all relevant data collected during Part 2.

7.3.1.2 Primary endpoint analyses for Part 2

The primary endpoint for Part 2 of the trial is OR defined by confirmed CR or PR according to RECIST 1.1 for all cohorts except GBM as assessed by the Investigator. OR in GBM cohort will be evaluated using RANO criteria. Overall response will be analyzed in terms of the shrinkage estimator of the OR rate (ORR) based on BHM.

Note on primary endpoint analysis in cohort F:

In addition, OR from stage I and stage II will be analyzed separately using a Bayesian approach with meta-analytic predictive (MAP) prior after completion of stage II. Please refer to [Section 7.1.2](#) for more details on the derivation of the MAP prior and the final decision criterion. A naïve estimate (observed objective response rate) along with 95% CI (Clopper-Pearson) will also be provided.

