Nugget 1: (20,20,5,15,20,5)	Cohort G: <20% (<3 out of 15)	40%/40%/83%/60%/40%/83%
Nugget 2: (20,20,25,15,20,5)	Cohort H: <7% (<2 out of 15)	40%/40%/8%/60%/40%/83%
Nugget 3: (40,40,25,35,40,25)		3%/3%/8%/6%/3%/8%

Table 7.7.2: 2

Operating characteristics of the Bayesian Hierarchical Modelling approach for final analysis under different scenarios with futility evaluation at the interim

Sample size	Scenario (ORR (%) in each patient cohort)	Probability of shrinkage estimator of the ORR \geq (20%,20%, 35%,35%, 20%,30%, 35%,20%) in at least one cohort at final	Probability of shrinkage estimator of the ORR \geq (20%,20%, 35%,35%, 20%,30%, 35%,20%) in each cohort at final	Probability of shrinkage estimator of the ORR \geq (25%,25%, 40%,40%, 25%,35%, 40%,25%) in at least one cohort at final	Probability of shrinkage estimator of the ORR \geq (25%,25%, 40%,40%, 25%,35%, 40%,25%) in each cohort at final
(40,40, 30,30, 30,30, 30,30)	Positive: (25,25,40,40,25,35,40,25)	99%	91%/91%/82%/82%/ 86%/82%/81%/85%	84%	49%/47%/47%/46%/ 46%/47%/46%/46%
	Negative: (5,5,20,20,5,15,20,5)	1.2%	0.0%/0.0%/0.2%/0.4%/ 0.0%/0.0%/0.6%/0.0%	0.3%	0.0%/0.0%/0.0%/0.1%/ 0.0%/0.0%/0.2%/0.0%
	Intermediate: (15,15,30,30,15,25,30,15)	30%	10%/8%/5%/6%/ 9%/6%/8%/7%	8%	1%/0.9%/1%/1%/ 0.8%/0.7%/2%/1%
	Nugget 1: (25,25,20,20,5,15,20,5)	77%	56%/58%/1%/0.7%/ 0.0%/0.6%/0.8/0.0%	49%	32%/28%/0.4%/0.1%/ 0.0%/0.1%/0.0%/0.0%
	Nugget 2: (25,25,20,20,25,15,20,5)	89%	63%/61%/1%/1%/ 58%/0.5%/1%/0.0%	65%	35%/34%/0.2%/0.3%/ 31%/0.0%/0.1%/0.0%
	Nugget 3: (5,5,40,40,25,35,40,25)	96%	0.0%/0.2%/59%/59%/ 61%/62%/60%/61%	80%	0.0%/0.0%/32%/32%/ 31%/32%/33%/31%
(30,30, 25,25, 25,25, 25,25)	Positive: (25,25,40,40,25,35,40,25)	99%	89%/89%/79%/79%/ 88%/81%/77%/87%	81%	49%/47%/46%/45%/ 47%/46%/46%/46%
	Negative: (5,5,20,20,5,15,20,5)	2%	0.0%/0.0%/0.5%/0.7%/ 0.0%/0.0%/1%/0.0%	0.3%	0.0%/0.0%/0.1%/0.1%/ 0.0%/0.0%/0.1%/0.0%
	Intermediate: (15,15,30,30,15,25,30,15)	34%	12%/9%/6%/7%/ 10%/7%/9%/9%	10%	2%/1%/1%/2%/ 1%/0.8%/2%/2%
	Nugget 1: (25,25,20,20,5,15,20,5)	69%	50%/50%/2%/1%/ 0.0%/0.9%/0.9%/0.0%	45%	29%/27%/0.3%/0.3%/ 0.0%/0.1%/0.1%/0.0%
	Nugget 2: (25,25,20,20,25,15,20,5)	84%	57%/55%/1%/1%/ 53%/1%/1%/0.0%	63%	32%/30%/0.3%/0.3%/ 29%/0.0%/0.4%/0.0%
	Nugget 3: (5,5,40,40,25,35,40,25)	93%	1%/1%/54%/54%/ 61%/59%/56%/62%	75%	0.0%/0.0%/31%/31%/ 30%/30%/31%/30%

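### Section 7.1.2 says the hierarchical prior gives only little borrowing, but Table 7.7.2: 2 shows cohort A's success probability moving from 91% to 56% through the other cohorts alone

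*Protocol*

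**What the plan says.** Protocol section 7.1.2 models the cohort log-odds, each offset by a target rate, as fully exchangeable. The prior on the overall mean is described thus: "A non-informative normal distribution with mean 0 and standard deviation of 2 is specified for the mean". For the heterogeneity parameter, "a half normal distribution with parameter 1 is used", and the text goes on to describe this choice: "which is a very conservative assumption regarding between-cohort variability and hence leads to only little borrowing of data across patient cohorts". The offset "is the target response rate", but section 7.1.2 gives no numbers for it.

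Section 7.3.1.2 makes the model output the primary analysis: "Overall response will be analyzed in terms of the shrinkage estimator of the OR rate (ORR) based on BHM". An observed rate with a Clopper-Pearson interval is stated there only in the note on cohort F.

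Table 7.7.2: 2 gives operating characteristics for cohorts A to H at sizes "40,40, 30,30, 30,30, 30,30". In the Positive row the probabilities that each cohort's shrinkage estimate reaches its first threshold (20% for A and B) are "91%/91%/82%/82%/ 86%/82%/81%/85" per cent. In the Nugget 1 row A and B have 56% and 58%.

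**The concern.** If borrowing were small, a cohort's chance of reaching its threshold would depend almost entirely on its own size and its own true rate. The table offers a clean test, because some pairs of rows leave a cohort's own conditions untouched and change only the others. In those pairs the probability moves a great deal.

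This matters for how the primary result is read. Section 1.3 says that response rates were judged against published results for each indication. Published rates are ordinarily not shrunk towards other tumour types. A reader who trusts section 7.1.2 would take the shrinkage estimate as close to the cohort's own observed rate and compare the two directly. For an active cohort among inactive ones that comparison is biased downwards.

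**Working it through.** **Inputs, all from the protocol.** Cohort sizes, true rates, thresholds and probabilities come from Table 7.7.2: 2. Section 7.4 limits the interim futility analysis to cohorts C to H, so cohort A always contributes its full 40 patients. The priors come from section 7.1.2.

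**Step 1. What differs between the rows.** Positive has true rates (25, 25, 40, 40, 25, 35, 40, 25)%. Nugget 1 has (25, 25, 20, 20, 5, 15, 20, 5)%. A and B are identical in the two rows; only C to H change.

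**Step 2. No-borrowing benchmark for cohort A.** The threshold is 20% × 40 = 8 responders. P(X ≥ 8 | n = 40, p = 0.25) = 0.818. This holds in both rows.

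**Step 3. Comparison with the table.**

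| Cohort A | Positive | Nugget 1 | Swing |
|---|---|---|---|
| Table 7.7.2: 2 | 91% | 56% | 35 points |
| No borrowing | 81.8% | 81.8% | 0 |
| Difference | about +9 | about −26 | |

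**Step 4. Not a single odd cell.**
- Cohort B goes from 91% to 58% between the same two rows.
- Nugget 3 differs from Positive only in A and B, which drop to 5%. Cohort C falls from 82% to 59% and cohort E from 86% to 61%. Without borrowing, C needs 35% × 30 = 10.5, so 11 responders, and must pass its interim (at least 3 of 15): 70.6% in both rows. E needs 6 of 30 and at least 2 of 15 at the interim: 77.4% in both.
- Nugget 2 differs from Nugget 1 only in cohort E, yet A moves from 56% to 63%.
- With the smaller sample sizes in the table, A goes from 89% to 50%. The no-borrowing value is P(X ≥ 6 | 30, 0.25) = 79.7%.

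**Step 5. Simulating the stated model.** Target rates had to be assumed. They were set at background plus 20 points, that is (25, 25, 40, 40, 25, 35, 40, 25)%. Taken literally (posterior mean, stopped cohorts kept in the model), the simulation gives cohort A 93.0% in Positive and 50.8% in Nugget 1, against the printed 91% and 56%. Posterior median instead of mean, dropping stopped cohorts, placing the prior on the variance, or using the thresholds as target rates gives swings of about 28 to 47 points. None is small. With target rates at background, A comes out at 58% in Positive, which does not fit the printed 91%, so that offset was evidently not used.

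**Step 6. Effect on the estimate.** Take 10/40 = 25% observed in cohort A, the same assumed target rates, and cohorts C to H at their background rates. The posterior mean for A is about 17% if B is also at background (2/40) and about 19% if B also has 10/40. If all other cohorts are at their positive rates it stays at about 25%.

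**Why a wide prior still borrows.** When the cohorts agree, the posterior mean of the heterogeneity parameter falls to about 0.13. The data then pull the model towards pooling, and the half-normal(1) prior does little to resist.

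**The case against.** The strongest defence is that 'little' is relative and that the metric exaggerates. In the same simulation, tighter half-normal priors give cohort A lower Nugget 1 probabilities still: 44% with parameter 0.5, 26% with 0.25 and 7% with 0.125. The chosen prior borrows least of these. The 35-point swing is also a change in the chance of crossing a cut-off (20%) close to the true rate (25%). On the estimate itself the mean bias in Nugget 1 is about −3 to −4 points, roughly half the binomial standard error of √(0.25 × 0.75 / 40) = 6.8 points. The protocol also discloses exchangeability and prints about 60% true-positive probability for nugget scenarios.

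All of that stands, and it makes a relative claim defensible. It does not rescue an absolute claim of only little borrowing, and the protocol does not show that the figure of about 60% compares with 81.8% for cohort A analysed alone.

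Several stronger readings are tempting but not supported:
- *Inactive cohorts are pulled up.* In the nugget rows at the planned sizes they reach their threshold in about 1% of trials or fewer. In a re-fit with cohort F at 12/30 and the others at background, cohorts at 5% rise only to about 8%, and those at 20% move slightly down, to about 19%.
- *Shrinkage hides activity in cohort F.* That cohort has its own naïve estimate with an exact interval and a separate stage II analysis, and section 3.1 cites its unshrunken 40%.
- *A cohort could be declared negative on the shrinkage estimate.* No protocol rule does this; futility uses the observed rate, and section 7.2 calls all analyses descriptive and exploratory.
- *Table 7.7.2: 2 is wrong.* The simulation does not match it exactly, but the target rates, the choice of mean or median and the handling of stopped cohorts are unstated, so no error can be inferred.
- *The observed rate is missing for the other cohorts.* The statistical analysis plan, which was not available, may provide it. Its absence here is not the finding.

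**Conclusion.** The description in section 7.1.2 is contradicted by the protocol's own operating characteristics. For cohort A borrowing adds about 9 points to the success probability in one row and removes about 26 in another, with nothing about A or B changed. This rests on printed figures and one binomial probability, and needs no assumption about the target rates.

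The shrinkage of 10/40 to roughly 17 to 19% does depend on assumed target rates of background plus 20 points, and is an indication of size only. The cost is mainly that an active cohort among inactive ones is estimated too low and missed more often; false positives are well controlled. The prior itself may be kept. What should change is its description and what is shown beside the estimate. Enrolment has stopped, but section 8.6 places the final report after all patients have completed, so the change can still affect how the results are read.

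**What to change.** In section 7.1.2, delete the statement that the prior is very conservative and gives only little borrowing. State instead how far the cohort probabilities in Table 7.7.2: 2 depend on the other cohorts, and add the no-borrowing probabilities to that table (81.8% for cohort A in Positive and Nugget 1). If a comparison with other priors is wanted, say that this prior borrows less than a half-normal with a smaller parameter.

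In section 7.3.1.2, report the observed response rate with a Clopper-Pearson 95% interval for every cohort beside the shrinkage estimate, as is already planned for cohort F and, in section 7.3.2.2, for disease control.

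The cost is one rewritten sentence, the added benchmark figures and two columns in the results table. No new data or change of model is needed. The drawback is that the cohort-specific intervals are wider than those from the hierarchical model, so the report will show more uncertainty per cohort.
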